3.8 Height and Weight

Height will be measured at Screening only, with shoes removed. Body weight will be measured at scheduled visits as specified in Section 2. It is recommended that the subject wear lightweight clothing and no shoes during weighing.

3.9 Vital Signs

Vital sign determinations of body temperature, respiration rate, pulse rate, and systolic and diastolic blood pressure will be obtained at visits as specified in Section 2. Blood pressure, pulse rate and respiratory rate should be measured after the subject has been sitting for at least 5 minutes.

3.10 Physical Examination

A complete physical examination (excluding genitourinary) will be performed at the Screening visit as specified in Section 2. Subsequent physical examinations will be limited to evaluations of throat, chest, and heart. At any time, a symptom-directed physical examination can be performed as deemed necessary by the investigator. The physical examination performed on Study Day 1 will serve as the baseline physical examination for the entire study. Any significant physical examination findings after the first dose will be recorded as AEs. All findings, whether related to an AE or part of each subject's medical history, will be captured on the appropriate eCRF page.

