2.2 Benefits and Risks to Subjects

The safety results from Phase 1 studies demonstrated that ABBV-2222 and ABBV-3067 were generally well tolerated in healthy volunteers, either as single agent or combination regimen.

ABBV-2222 treatment in vitro improved CFTR channel expression and function in HBE cells. The completed Phase 2 study (Study GLPG2222-CL-202) showed that 4-week treatment of ABBV-2222 significantly reduced SwCl in CF subjects homozygous for F508del mutation. Preliminary results from the ongoing Phase 1 study (Study GLPG2737-CL-105) also showed that the dual combination of

ABBV-2222 and GLPG2451 (another potentiator under development with a similar mechanism of action as ABBV-3067) reduced SwCl and increased ppFEV₁ in patients with CF who are homozygous for the F508del mutation. Therefore, it is anticipated that the combination of ABBV-2222 and ABBV-3067 has the potential to improve F508del CFTR function in patients with CF, as well as their lung function measured by ppFEV₁.

The following paragraphs describe the main risks that are potentially associated with repeated doses of ABBV-2222, in combination with potentiator/corrector compounds (GLPG2451, ABBV-3067, and [REDACTED]).

Rash

Nonserious adverse events (AEs) of rash of mild to moderate severity have been observed following multiple-dose treatment with ABBV-2222 in combination with ABBV-3067 or GLPG2451, [REDACTED]. Rash was considered possibly related to study drug by the investigator and resolved after treatment discontinuation.

There were also reports of mild rash occurring among subjects who received ABBV-2222 alone, but none led to study drug discontinuation.

As a result of these rash occurrences, enhanced safety monitoring and specific guidance to the investigator is described in the Operations Manual ([Appendix F](#)). Rash is considered an adverse event of special interest (AESI) (see Section [6.1](#)).

Taken together, the safety and efficacy data from the Phase 1 and Phase 2 programs support further development of ABBV-3067 and ABBV-2222 in Phase 2 studies in subjects with CF.

For further details, please see findings from completed studies, including safety data in the ABBV-3067 and ABBV-2222 Investigator's Brochures.¹⁻²

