Hospitalization or Prolongation of Hospitalization	An event that results in an admission to the hospital for any length of time or prolongs the subject's hospital stay. This does not include an emergency room visit or admission to an outpatient facility.
Congenital Anomaly	An anomaly detected at or after birth, or any anomaly that results in fetal loss.
Persistent or Significant Disability/Incapacity	An event that results in a condition that substantially interferes with the activities of daily living of a study subject. Disability is not intended to include experiences of relatively minor medical significance such as headache, nausea, vomiting, diarrhea, influenza, and accidental trauma (e.g., sprained ankle).
Important Medical Event Requiring Medical or Surgical Intervention to Prevent Serious Outcome	An important medical event that may not be immediately life-threatening or result in death or hospitalization, but based on medical judgment may jeopardize the subject and may require medical or surgical intervention to prevent any of the outcomes listed above (i.e., death of subject, life threatening, hospitalization, prolongation of hospitalization, congenital anomaly, or persistent or significant disability/incapacity). Additionally, any elective or spontaneous abortion or stillbirth is considered an important medical event. Examples of such events include allergic bronchospasm requiring intensive treatment in an emergency room or at home, blood dyscrasias or convulsions that do not result in inpatient hospitalization, or the development of drug dependency or drug abuse.

All AEs reported from the time of study drug administration until 30 days or 5 half-lives after discontinuation of study drug administration will be collected, whether solicited or spontaneously reported by the subject. In addition, SAEs and protocol-related nonserious AEs will be collected from the time the subject signs the study-specific informed consent.

AbbVie will be responsible for suspected unexpected serious adverse reactions (SUSAR) reporting for the investigational medicinal product (IMP) in accordance with global and local requirements.

Adverse events will be monitored throughout the study to identify any of special interest that may indicate a trend or risk to subjects.

Adverse Events of Special Interest

Rash is an AE of special interest (AESI) and will be monitored during the study.

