APPENDIX D. ACTIVITY SCHEDULE

The following table shows the required activities across the study visits. The individual activities are described in further detail in the Operations Manual.

Study Activities Table

Activity	Screening Period	Treatment Period				Follow-Up Period
	UP to Day -30	Day 1	Day 7 (phone call) (± 2 days)	Day 15 (± 2 days)	Day 29 (± 2 days) or Premature Discontinuation	30-Day Follow-Up (± 7 days)
INTERVIEWS & QUESTIONNAIRES						
Informed consent	✓					
Eligibility criteria	✓	✓				
Medical/surgical history	✓					
Adverse event assessment	✓	✓	✓	✓	✓	✓
Prior/concomitant therapy	✓	✓	✓	✓	✓	✓
Time of last dose of bronchodilator (if applicable)	✓	✓		✓	✓	✓
Date and time of previous 3 doses of study drug				✓	✓	
LOCAL LABS & EXAMS						
Height	✓					
Weight	✓	✓			✓	✓
Vital signs (include oral temperature, respiratory rate, heart rate, and blood pressure)	✓	✓		✓	✓	✓
Pulse oximetry	✓	✓		✓	✓	✓
Physical examination (full)	✓					
Physical examination (limited to throat, chest, heart)		✓		✓	✓	✓
Urine pregnancy test (females of childbearing potential only; to be followed by serum pregnancy test only if urine test is positive)		✓			✓	✓
12-lead ECG (after at least 5 minutes of rest while supine)	✓			✓	✓	
Sweat collection (send sample to central laboratory)	✓	✓		✓	✓	✓
Spirometry (on Days 1 and 15, pre-dose [0 hr] and 3 - 5 hr following dose). Numbers in parentheses indicate the number of tests.	✓	✓ (2)		✓ (2)	✓	✓
CENTRAL LABS						
CFTR Genotyping	✓					

Activity	Screening Period	Treatment Period				Follow-Up Period
	UP to Day -30	Day 1	Day 7 (phone call) (± 2 days)	Day 15 (± 2 days)	Day 29 (± 2 days) or Premature Discontinuation	30-Day Follow-Up (± 7 days)
Urine test for drugs of abuse	✓					
Serology for HBsAg, HCV, HIV-1 and HIV-2 antibodies	✓					
Serum pregnancy test (females of childbearing potential only)	✓					
High-sensitivity C-reactive protein (hsCRP), clinical chemistry, hematology (complete blood count), urinalysis	✓	✓		✓	✓	✓
Follicle-stimulating hormone (FSH) (postmenopausal females ≤ age 55 years only)	✓					
Blood samples for ABBV-3067 and ABBV-2222 pharmacokinetic assay (Day 15 samples pre-dose [0 hour], 2, 4, and 6 hours following dose; Day 29 approx. 24 hours following last dose). Numbers in parentheses indicate the number of samples to be drawn.				✓ (4)	✓ (1)	✓ (1)
Optional biomarker sample: Whole blood		✓			✓	
Rx TREATMENT						
Randomization/drug assignment		✓				
Dispense study drugs		✓		✓		
Perform drug reconciliation				✓	✓	

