 EXAM	
 • Weight • Vital signs^a • Limited physical examination^b 	
 • Pulse oximetry^a • Sweat collection • Spirometry^c
 LAB	
 • Urine pregnancy test 	
 CENTRAL LAB	
 • hsCRP, clinical chemistry, hematology (CBC), and urinalysis • Serum pregnancy test^d 	
 • Optional biomarker sample: whole blood
 TREATMENT	
 • Randomization/drug assignment • Dispense study drug 	
 • Study drug administered at the site after a meal

NOTES:

- a. Vital signs (Includes oral temperature, respiration rate, heart rate, blood pressure) and pulse oximetry after at least 5 minutes of rest.
- b. Includes throat, chest, heart, and symptom-directed exam.
- c. Pre-dose (0 hour) and 3 to 5 hours following dose.
- d. Only for confirmation if urine test is positive.

DAY 7 (Phone call only ± 2 days):

 INTERVIEW	
 • AE assessment • Prior/concomitant therapy
---	--

DAY 15 (± 2 days):

	INTERVIEW	
 • AE assessment • Prior/concomitant therapy 	
 • Collect date and time of previous 3 doses of study drug • Time of last dose of bronchodilator (if applicable)
	EXAM	
 • Vital signs^a • Limited physical examination^b • 12-lead ECG^c 	
 • Pulse oximetry^a • Sweat collection • Spirometry^d
	CENTRAL LAB	
 • hsCRP, clinical chemistry, hematology (CBC), and urinalysis 	
 • Blood samples for ABBV-3067 and ABBV-2222 plasma concentrations assay^e
	TREATMENT	
 • Dispense study drug • Perform drug reconciliation 	
 • Study drug administered at the site after a meal

NOTES:

- a. Vital signs (Includes oral temperature, respiration rate, heart rate, blood pressure, preferably before blood draw) and pulse oximetry after at least 5 minutes of rest.
- b. Includes throat, chest, heart, and symptom-directed exam.
- c. After at least 5 minutes of rest while supine, preferably before blood draw.
- d. Pre-dose (0 hour) and 3 to 5 hours following dose.
- e. Pre-dose (0 hour) and 2, 4, and 6 hours following dose.

DAY 29 (± 2 days) or

PREMATURE DISCONTINUATION:

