4.2 Recording Data and Analyses of Safety Findings

AEs will be coded using the Medical Dictionary for Regulatory Activities (MedDRA). The number and percentage of subjects with treatment-emergent adverse events (i.e., any event that begins or worsens in severity after initiation of study drug through 30 days post-study drug dosing) will be tabulated by primary MedDRA System Organ Class (SOC) and preferred term (PT). The tabulation of the number of subjects with treatment-emergent AEs by severity grade and relationship to study drug also will be provided. Subjects reporting more than 1 AE for a given MedDRA preferred term will be counted only once for that term using the most severe grade according to the severity grade table and the most related according to the relationship to study drug tables. Subjects reporting more than 1 type of AE within an SOC will be counted only once for that SOC.

Adverse Events of Special Interest

Isolated instances of nonserious, generalized, maculopapular rash have occurred in prior Phase 1 studies when ABBV-3067 and ABBV-2222 were administered together (see protocol Section 6.1). All rash AEs are considered adverse events of special interest (AESIs). These AEs have to be reported in real time (i.e., within 24 hours from the time of the knowledge of the event) using a study-specific rash questionnaire ([Appendix B](#)).

Maculopapular and other rash events are to be graded as follows (adapted from Common Terminology Criteria for Adverse Events [CTCAE] version 5.0):

- Grade 1** Macules/papules covering < 10% body surface area (BSA) with or without symptoms (e.g., pruritis, burning, tightness).
- Grade 2** Macules/papules covering 10% to 30% BSA with or without symptoms (e.g., pruritis, burning, tightness); or rash covering > 30% BSA with or without mild symptoms.
- Grade 3** Macules/papules covering > 30% BSA with moderate or severe symptoms.

Note: To calculate the percent of BSA, estimate the area covered by the actual macules/papules and do not include the clear skin between them. Imagine the rash coverage as if all of the macules and papules

coalesce into a single area. A diagram showing the contribution of different body parts to BSA, helpful to calculate % BSA, can be found at:

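### Rash is the only adverse event of special interest, but no scheduled examination after Screening names skin, so the Day 1 baseline has no planned skin finding

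*Protocol*

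**What the plan says.** Protocol 6.1 states: "Rash is an AE of special interest (AESI) and will be monitored during the study". Neither the Protocol, the Operations Manual (Protocol Appendix F) nor the SAP names any other event of special interest. Protocol 2.2 describes rash seen in earlier studies and continues: "As a result of these rash occurrences, enhanced safety monitoring and specific guidance to the investigator is described in the Operations Manual".

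On examinations, Operations Manual 3.10 says: "A complete physical examination (excluding genitourinary) will be performed at the Screening visit". For later visits it says: "Subsequent physical examinations will be limited to evaluations of throat, chest, and heart". It also says: "The physical examination performed on Study Day 1 will serve as the baseline physical examination for the entire study". The Protocol Appendix D row reads "Physical examination (limited to throat, chest, heart" and is ticked for Day 1, Day 15, Day 29 or Premature Discontinuation, and the 30-day follow-up. The notes to those same visits in Operations Manual 2.1 and 2.2 are wider: "Includes throat, chest, heart, and symptom-directed exam". Section 3.10 also permits a symptom-directed examination at any time, at the investigator's discretion.

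Operations Manual 4.2 grades rash by the body surface area (BSA) covered and by symptoms. Grade 1 is "Macules/papules covering < 10% body surface area (BSA) with or without symptoms". Grade 2 also does not require symptoms, and it includes rash over more than 30% BSA with no more than mild symptoms.

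**The concern.** Protocol 2.2 leads the reader to expect a planned way of looking for rash. What the Operations Manual contains is a grading scale, 24-hour reporting, a questionnaire, a discontinuation statement and optional further investigation. Each of these starts once a rash is already known.

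Three uses of the data are affected.

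- **Dose choice.** Safety from Part 1 is a stated input to the ABBV-2222 dose for Part 2 (Protocol 3.1 and 4.1).
- **Counting.** SAP 9.2.5 identifies rash by a query on recorded adverse event terms, so a rash that was never recorded cannot be counted. Operations Manual 3.10 sends significant examination findings into the adverse event record, but skin lies outside the scheduled part of that route.
- **Hepatic criterion.** Rash is one of the signs which, together with AST or ALT above 3 × ULN, meets a hepatic discontinuation criterion in Protocol 5.5.

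**Working it through.** The plan states no rash rate and no detection rate, so there is no figure to reproduce. The check is a comparison of passages and a count.

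**1. Count of examinations (Protocol Appendix D; Operations Manual 2.1, 2.2 and 3.10)**

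| Visit | Scope of physical examination | Skin named? |
|---|---|---|
| Screening (up to 30 days before Day 1) | Complete, except genitourinary | Not named separately, but within a complete examination |
| Day 1 (declared baseline) | Throat, chest, heart, symptom-directed | No |
| Day 15 | Same | No |
| Day 29 or Premature Discontinuation | Same | No |
| 30-day follow-up | Same | No |

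Five on-site visits have an examination. One is complete and four are limited. None of the four names skin.

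**2. Does the symptom-directed part close the gap?** Only in part. It is triggered by a complaint or by the investigator's judgement. The scale in Operations Manual 4.2 admits symptom-free rash at Grade 1 and Grade 2, so some events that count as events of special interest need not set off the trigger.

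**3. Baseline.** Operations Manual 4.2 treats an event as treatment-emergent if it begins or worsens after study drug starts. Protocol 7.4 and SAP 9.2.1 go by onset date. The first definition needs the extent of any rash on Day 1; the second needs to know whether it was already there. The scheduled Day 1 examination supplies neither. Updated medical history on Day 1 (Operations Manual 3.2) helps, but it is not an examination.

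**4. Weight of one event.** Arm sizes are 9 or 18 (Protocol 4.1).

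- Arm of 18: 1/18 = 5.6 percentage points
- Arm of 9: 1/9 = 11.1 percentage points

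This holds for any single adverse event. It shows how coarse the arm-level rates are and is not an estimate of how many rashes would be missed.

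**5. Consistency across sites.** About 189 subjects at about 59 sites gives 189/59 = 3.2 per site. Randomization is stratified by screening ppFEV₁ only. If sites differ in how closely they question or look, nothing in the design balances that difference across arms of 9 or 18. It would add noise; it would not be expected to favour any arm.

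**The case against.** Rash is visible, and there are several ways for it to come to light. Adverse events are assessed at every visit, including the Day 7 call, and are collected whether solicited or volunteered (Protocol 6.1 and Appendix D). Investigators are told to watch for clinical evidence of events routinely. The chest is examined at all four visits, and Protocol 6.1 describes maculopapular rash as often involving the upper trunk and associated with itching. Sweat is collected from both arms at the same visits. In the rash scale, symptoms means sensations such as itching or burning, so a symptom-free rash can still be seen and reported by the subject.

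Most of this stands, and it rules out four stronger readings that a reader might infer.

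- *Skin is never examined after Screening.* The visit notes include a symptom-directed examination. The documents support only that no skin examination is scheduled.
- *Symptom-free rash is found by self-report alone.* Questioning, routine monitoring and incidental observation also operate.
- *New and pre-existing lesions cannot be told apart.* There is a complete Screening examination, a Day 1 history update, and a rash questionnaire that asks about earlier skin disorders. Separation is less reliable, not impossible.
- *A subject with extensive symptom-free rash escapes the stopping rule.* The rash discontinuation statements concern Grade 3 (Operations Manual 4.2) or Grade 3 and above (Protocol 5.5). Grade 3 on the rash scale requires moderate or severe symptoms. A symptom-free rash is at most Grade 2 and would not meet the statement even if it were seen.

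The objection does not remove the core point. These routes are general or incidental, none is a planned look at the skin, and the examination called the study baseline omits the organ concerned in the one event of special interest.

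**Conclusion.** The point holds as a gap in ascertainment. For the only event of special interest, none of the four scheduled examinations after Screening names skin, and the Day 1 baseline has no planned skin finding. The enhanced monitoring announced in Protocol 2.2 takes the form of steps that begin after a rash is known.

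The likely effect is lower sensitivity and less uniform recording of symptom-free rash, and weaker judgement of whether an existing rash has worsened. Its size cannot be derived from the documents. Treatment is double-blind and the schedule is the same in every arm, so there is no evident mechanism for bias between arms; under-recording would mainly blunt the comparison. The conclusion assumes that sites follow the examination scope as written and that no instruction to inspect the skin exists outside the supplied text.

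**What to change.** Reconcile Protocol 2.2 with Protocol Appendix D and Operations Manual 2.1, 2.2 and 3.10.

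- Add skin to the limited examination at Day 1 (before dosing), Day 15, Day 29 or Premature Discontinuation, and follow-up, with the same wording in all of these places.
- Record rash as present or absent at each of these visits, and the percentage of BSA only if it is present.
- Name rash explicitly in the adverse event questions of the Day 7 call.

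Leave the grading scale, the discontinuation criteria and the management of rash as they are.

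The cost is revised wording, small eCRF additions and a few extra minutes in an examination that already takes place. No visit, staff or invasive procedure is added. Somewhat more low-grade rash will be recorded, in all arms including placebo, and the study report should expect this.

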3.11 Pulse Oximetry

Pulse oximetry is an indirect measurement of oxygen saturation in blood. It will be performed beginning at Screening and as specified in Section 2. Pulse oximetry should be measured after the subject has been sitting for at least 5 minutes.

3.12 Sweat Collection

Sweat collection will be performed to evaluate sweat chloride (SwCl). Sweat chloride concentration is a biomarker of CFTR ion channel function. It is a sensitive, standardized and non-invasive measure to assess systemic CFTR modulator effects. Chloride concentration will be measured in sweat collected by an approved collection device provided to sites by a central provider and according to the 2009 guidelines issued by the Clinical and Laboratory Standards Institute.

To ensure consistency and reproducibility in this multicenter study, trained clinical study centers will collect sweat according to procedures as outlined in the lab manual. Two sweat collections, one from

each arm, will be obtained from each subject at the time points indicated in the protocol activity schedule. Sweat samples will immediately be frozen and sent to the central laboratory for testing and interpretation of results.

The clinical study center should be encouraged to select subjects for the study for which it is known that adequate quantities of sweat can be collected.

The sites will be provided with sweat collection equipment and kits, and a central laboratory will act as central readers for SwCl. Sweat collection will be measured beginning at Screening and as specified in Section 2.

To prevent the potential unblinding, site personnel and subjects will not be informed of the subjects' study-related post-first-dose sweat chloride results until the end of the corresponding study part (Part 1 or Part 2).

3.13 Spirometry

Spirometry will be performed to assess pulmonary function beginning at Screening and as specified in Section 2. At the Day 1 and Day 15 visits, spirometry must be performed pre-dose and between 3 and 5 hours following dosing.

The spirometry test must meet the criteria for acceptability and repeatability as defined in the 2005 American Thoracic Society/European Respiratory Society (ATS/ERS) guidelines on standardization of lung function testing.¹

Consistency is very important for subjects who take bronchodilators and perform airway clearance on a regular basis, since they may have short-term effects on FEV₁, the primary endpoint for this study. Please refer to Section 5.4 of the protocol for detailed guidance on the timing of dosing for these therapies relative to spirometry.

The following parameters will be measured as part of the spirometry assessment:

- FEV₁ (L) and percent predicted FEV₁ for age, gender, and height;
- Forced vital capacity (FVC) (L) and percent predicted FVC for age, gender, and height;
- FEV₁/FVC ratio;
- Forced expiratory flow between 25% and 75% of exhaled volume (FEF₂₅₋₇₅).

Predicted values will be estimated using the 2012 Global Lungs Initiative equation.²

The vendor will provide the sites with spirometers and will act as the central reader for spirometry results.

To prevent the potential unblinding, subjects will not be informed of their study-related spirometry results until the end of the corresponding study Part (Part 1 or Part 2).

